**Table 1: Minimal Detectable Percentage of Immune Responders by Sample Size**

Total Sample Size	Sample Size per Subgroup	Immune Responders (Smallest % in Either Subgroup)	Minimum Detectable Difference (%)
1000	900/100	20%	15%
1000	900/100	50%	17%
1000	900/100	80%	12%
500	450/50	20%	22%
500	450/50	50%	23%
500	450/50	80%	16%
200	180/20	20%	36%
200	180/20	50%	35%
200	180/20	80%	20%

## 7.2.2 Exploratory Analyses

For subjects concurrently enrolled in Dendreon-sponsored trials in which OS data are collected, the association of this endpoint and the individual immune response assays will be assessed using a Cox proportional hazards regression model. Key subgroups of interest will be defined on the basis of baseline demographics and disease characteristics (e.g., age, race, ECOG status, and serum PSA). Similar analyses may be conducted should sufficient data for other clinical endpoints be available from the trial(s) in which subjects are concurrently enrolled.

The association between immune response and sipuleucel-T product parameters (APC activation, APC count, and TNC count) will be assessed using logistic regression. The correlation between individual immune response assays and cumulative sipuleucel-T product parameters will also be summarized.

The relationship between gene expression profile at various time points and OS will be assessed using Cox proportional hazards regression models.

Repeated measurement mixed models will be used to explore genomic parameters and the profile of gene expression parameters over time to potentially provide insights into the immune response as it relates to the mechanism of action of sipuleucel-T. Transformation of the gene expression parameters may be applied if the original data are not normally distributed. Groupings of genes (e.g., 2-gene models) will also be explored.

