**Statistical Considerations:** The primary endpoint is the percentage of subjects who exhibit any immune response at any post-treatment time point (6, 10, 14, 26, 39, and 52 weeks after the first infusion of sipuleucel-T). Logistic regression will be used to explore the effects of baseline characteristics on the primary endpoint. The association between the primary endpoint and cumulative sipuleucel-T product parameters (APC activation, APC count, and TNC count) will be assessed using logistic regression. The correlation between individual immune response

assays and cumulative sipuleucel-T product parameters will also be summarized. For Dendreon-sponsored studies in which data on OS are collected, the association of this endpoint and the individual immune response assays will be assessed using a Cox proportional hazards regression model.

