### **2.2 Exploratory Objectives**

- Where OS data are collected in the concurrent Dendreon-sponsored trial or registry, to evaluate the relationship between OS and immune response
- To explore the relationships between sipuleucel-T product parameters (APC activation, APC count, and TNC count) and immune response
- To explore relationships between OS and genomic or gene expression profiles

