## **3.0 STUDY ENDPOINTS**

### **3.1 Primary Endpoint**

The percentage of subjects who exhibit any immune response at any post-treatment timepoint (6, 10, 14, 26, 39, and 52 weeks after the first infusion of sipuleucel-T) on the basis of:

- Interferon-gamma (IFN $\gamma$ ) enzyme-linked immunospot (ELISPOT) response to PAP or PA2024
- T cell proliferation response to PAP or PA2024
- Anti-PAP or anti-PA2024 humoral response

Antigen-specific T cell responses will be assessed using assays such as, but not limited to, H-thymidine uptake to measure the capacity of T cells to proliferate in response to antigen

stimulation, and IFN $\gamma$  ELISPOT. The functional phenotypes of T cell subsets will be investigated using polychromatic flow cytometric analysis. Antigen-specific humoral responses will be measured using techniques such as enzyme-linked immunosorbent assay (ELISA).

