## 7.2 Statistical Analysis

### 7.2.1 Primary Analysis

The primary endpoint is the percentage of subjects who exhibit an immune response at any post-treatment time point (6, 10, 14, 26, 39, and 52 weeks after the first infusion of sipuleucel-T). The primary immune response analysis population will include all subjects who receive all 3 infusions of sipuleucel-T; summaries will also be generated for the population of patients who receive at least one partial infusion of sipuleucel-T. Logistic regression will be used to explore the effect of baseline characteristics on the primary endpoint. Repeated measurement mixed models will be used to explore the individual immune response assays as continuous endpoints over time. Transformation of the continuous outcome may be applied if the original data are not normally distributed. Key subgroups of interest will be defined on the basis of baseline demographics and disease characteristics (e.g., age, race, ECOG status, and serum PSA).

Table 1 summarizes the minimum detectable percent difference in immune responders with 90% power using a two independent proportions test at the two-sided 0.05-level between two subgroups, with the smaller subgroup representing 10% of total sample size and a minimum immune response incidence in each subgroup of 20% to 80%. In the IMPACT study, 79% of sipuleucel-T subjects had an immune response by any of the 3 assays to either PA2024 or PAP at any time point post-baseline (Sheikh 2013).

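### Section 7.2.2 does not say when immune response is classified for the Cox model of OS; any-visit status or a peak value used as a fixed covariate could create an apparent survival benefit, and a landmark would prevent it

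*Combined protocol and SAP*

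**What the plan says.** Relating survival to response is an exploratory objective: Section 2.2 aims "to evaluate the relationship between OS and immune response" where the concurrent Dendreon-sponsored trial or registry collects OS. Section 7.2.2 gives the method: "the association of this endpoint and the individual immune response assays will be assessed using a Cox proportional hazards regression model". The Statistical Considerations part of the synopsis repeats it, opening with "For Dendreon-sponsored studies in which data on OS are collected".

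The response definition is in Section 3.1, "The percentage of subjects who exhibit any immune response at any post-treatment timepoint", and again in Section 7.2.1, "The primary endpoint is the percentage of subjects who exhibit an immune response at any post-treatment time point". Both list weeks 6, 10, 14, 26, 39 and 52 after the first infusion. The per-assay responder rule in Section 7.1.1 compares an observed result with a threshold and names no visit. Section 7.2.1 also plans a continuous analysis of the assays: "Repeated measurement mixed models will be used to explore the individual immune response assays as continuous endpoints over time". That sentence concerns assay levels over time, not OS.

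On populations, Section 7.2.1 says "The primary immune response analysis population will include all subjects who receive all 3 infusions of sipuleucel-T", and adds that "summaries will also be generated for the population of patients who receive at least one partial infusion of sipuleucel-T". Neither sentence is tied to the OS model.

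For the OS model, the document gives no classification visit, landmark, time-dependent term or rule for men who stop being sampled.

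**The concern.** A man can be recorded as a responder only if he lives long enough to give a positive sample. Suppose status over the whole of weeks 6 to 52 is treated as if it were known at the start. The time a responder survived before his first positive sample then counts as responder survival, while men who die early have fewer visits at which to respond and stay in the non-responder group. The fitted HR falls below 1 even when response and survival are unrelated. The maximum of a continuous assay over all visits has the same fault, because longer survivors contribute more values to the maximum.

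At stake is the interpretation of any OS association from this study. Sections 1.1.2.1 and 1.2 cite an earlier correlation between immune response and OS, so a result produced by timing alone could be taken as confirmation. The primary percentage of responders does not depend on this model.

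**Working it through.** The plan gives no HR, event count or power for this model, so there is no figure of its own to reproduce. The check is a simulation in which response has no effect on OS.

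**Inputs from the document**
- Median OS 25.8 months: sipuleucel-T arm of the pivotal trial, Section 1.1.2.1.
- Any-visit response 79%: Section 7.2.1.
- Visits at weeks 6, 10, 14, 26, 39 and 52: Section 3.1.
- Three doses about 2 weeks apart (Section 4.0), so the third falls near week 4. The three-infusion population is therefore alive at about week 4.
- N=500: one of the illustrative sizes in Table 1.

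**Assumptions**
- Exponential survival, censoring at 36 months, and 79% read as the rate if followed to week 52.
- Timing of first response is not documented, so a range is used. The shares over the six visits are: all at week 6; 80/8/5/3/2/2; 60/15/10/6/5/4; a constant per-visit rate; an even spread.

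**Early deaths.** P(death by t) = 1 − exp(−ln 2 × t / 25.8), t in months, 52 weeks = 12 months.
- Week 6 (1.38 months): 3.7%.
- Week 14 (3.23 months): 8.3%. For men alive at week 4 (10 weeks, 2.31 months): 6.0%.
- Week 52 (12 months): 27.6%.

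More than a quarter of men would die before the last visit that can make them responders.

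**Fixed any-visit covariate, true HR 1.00, only death stops sampling** (false rejection at two-sided 0.05, N=500)

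| First responses | Men alive at week 6 | Men alive at week 4, unsampled counted as non-responders |
|---|---|---|
| All at week 6 | 1.00 (5%) | 0.91 (13%) |
| 80% at week 6 | about 0.90 (about 15%) | 0.82 (34%) |
| 60% at week 6 | about 0.79 (about 45%) | 0.73 (64%) |
| Constant per-visit rate | 0.66 (about 90%) | 0.62 (96%) |
| Even spread | 0.55 (about 100%) | 0.52 (100%) |

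Counting every man from first infusion, the range is 0.78 (51%) to 0.47 (100%).

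**Lower response rates.** Table 1's 50% and 20% are borrowed here as assumed single-assay rates, with 80% or 60% of first responses at week 6 and men alive at week 6. At 50% the HR is 0.95 or 0.90 (6% to 16% at N=500). At 20% it is 0.92 to 0.97 (5% to 7%).

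**Continuous assay.** Peak over all visits: HR per SD 0.82, 0.88 and 0.93 at assumed within-man correlations of 0.2, 0.5 and 0.8 (87%, 56% and 24% rejection at N=500). Value at week 6 or week 14 among men sampled then: 1.00 (4% to 6%). The same restriction matters for any fixed-visit marker. Giving men who died earlier a low value moves the HR, counted from first infusion, to 0.89 at week 6 and 0.44 at week 52.

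**Remedies at 79%, all timings**
- Only death stops sampling: the week-14 landmark and the time-dependent covariate both give 0.99 to 1.01 (4% to 6%).
- Section 6.2 lets sampling end while a man is alive, including on clinical judgment. If sampling stopped 4 or 13 weeks before death (assumed gaps), the time-dependent model gives 0.83 to 0.86 or 0.60 to 0.65. A landmark among all men alive gives 0.97 to 1.01 or 0.79 to 0.86. A landmark among men who gave the week-14 sample stays at 0.99 to 1.01.
- Limit of that landmark: if exit depends on response as well as prognosis, it gives 0.87 (only responders stop 13 weeks before death) or 1.15 (only non-responders do).

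**The case against.** The strongest reply is that the text may not plan the biased model at all. The OS sentence opens with OS, so *this endpoint* most naturally means OS, and the covariates are then the individual assays rather than the 79% composite. Section 7.2.1 treats those assays as continuous over time and Section 7.2.2 speaks of gene expression at various time points. Both fit per-visit models, which are unbiased among men sampled at the visit. This stands as far as it goes: the bias is permitted, not prescribed. It does not close the gap, because the individual assays have no classification time either, and Section 2.2 leaves the composite open as a covariate.

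Second, the size depends on timing that the document does not give, and on how men with no post-treatment sample are handled. Section 7.1.1 needs an observed result to declare a responder, so a man who died before week 6 may equally be unevaluable. This stands. It is why the main figures here are for men alive at week 6, and why they start at no bias.

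Third, the concurrent protocols, which are not available here, may define the OS time origin. A reader might infer that the origin is missing altogether; the document does not show that. Pooling across trials would still need one common origin for this analysis.

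Fourth, the sampling gaps before death are assumptions. Section 6.2 permits early exit but states no link to prognosis. They show how robust each remedy is and are not evidence of a defect.

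Last, the analysis is exploratory, with no alpha or power attached. That limits the priority.

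**Conclusion.** The gap is real and its consequence is conditional. If any-visit status or a peak value is used as a fixed covariate, the null HR among men alive at week 6 runs from 1.00 (all first responses at week 6) through about 0.90 and 0.79 to between 0.66 and 0.55 when responses are spread over visits. It is lower still if men who died before any sample count as non-responders, and closer to 1 at lower single-assay rates. These figures rest on exponential survival with a 25.8-month median, 79% response, censoring at 36 months and the assumed timings. With an assumed 60-month median, the range for men alive at week 4 is still 0.92 to 0.54.

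A reader might infer more: that the plan commits to a biased analysis, that any OS association it reports must be an artefact, or that the earlier correlation cited in Section 1.1.2.1 arose this way. The document supports none of these. It leaves the covariate open, a fixed-visit analysis among sampled men would be sound, and it does not describe how response was classified in the earlier work. Priority: consider, as a cheap improvement to an exploratory objective.

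**What to change.** In Section 7.2.2, and in matching synopsis wording:

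1. State that response for the OS models is classified at a prespecified landmark visit (for example week 14) from samples up to and including that visit, with OS counted from the landmark among men alive who gave that sample. Name the assay variable and the analysis population.
2. Add, as a sensitivity analysis, a time-dependent covariate that switches on at the first positive sample, with a stated rule for men whose sampling ends while they are alive.
3. Fit fixed-visit assay or gene expression models only among men sampled at that visit, with no value imputed for men who died earlier.
4. State the assumptions. The time-dependent model needs the end of sampling to be unrelated to prognosis. The landmark among sampled men needs exit not to depend on response and prognosis together. Section 5.3 helps here, since subjects and sites in Dendreon-sponsored trials do not receive the results.

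The cost is wording only, with no new samples or data. The downside is that a week-14 landmark loses about 6% of men alive at week 4, or 8% counted from first infusion, if only death stops sampling (13% to 15% if sampling stopped 13 weeks before death). Men who first respond later count as non-responders, and the result applies only to men still sampled at week 14.

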## 8.0 REPORTING REQUIREMENTS FOR SERIOUS ADVERSE EVENTS

Reporting requirements for serious adverse events (SAEs) are described in the respective protocol for the trial in which each subject is concurrently enrolled.

## 9.0 REGULATORY REQUIREMENTS

### 9.1 Required Documentation

Dendreon must receive the following P11-4 documentation prior to initiation of the study:

- Regulatory documents required by the trial in which the subject is concurrently enrolled
- Signed protocol signature page
- Signed Form FDA 1572
- Curriculum vitae of the Principal Investigator, updated within the past 2 years
- Copies of current medical licenses for the Principal Investigator and all sub-investigators

- Financial disclosure forms for the Principal Investigator and all sub-investigators
- Copy of Institutional Review Board (IRB) approval letter for study
- Copy of the IRB-approved ICF
- IRB Membership List or Department of Human and Health Services Assurance Number

## 9.2 Investigator Obligations

The Principal Investigator will be responsible for ensuring that all site personnel conduct the study in compliance with the Declaration of Helsinki and the ICH E6 Guideline for GCP, including the archiving of essential documents. The Principal Investigator will also ensure adherence to all national, state, and local laws of the pertinent regulatory authorities, including Federal regulations / guidelines set forth in 21 Code of Federal Regulations (CFR) § 11, 50, 54, 56, and 312.

The Principal Investigator will be responsible for the subject's compliance with the protocol, and may meet periodically with the Dendreon study monitor or Dendreon designee.

All investigators must complete and return financial disclosure statements (including information on spouses, legal partners, or dependent children) before study initiation. The investigators must promptly update this information if any relevant changes occur in the course of the study or in the year after the study is completed (21 CFR § 54.4). The investigators must promptly verify this information by completing and returning financial disclosure statements every 2 years throughout the study regardless of whether or not any information has changed.

In addition, the Principal Investigator is responsible for providing Dendreon an adequate final report shortly after he/she completes participation in the study, in accordance with 21 CFR § 312.64.

## 9.3 Subject Confidentiality

Individual subject medical information obtained as a result of this study is considered confidential and disclosure to third parties other than those noted below is prohibited. Subject's individual identifying information will be kept as confidential as possible under local, state, and federal law. Medical information may be given to the subject's personal physician or to other appropriate medical personnel responsible for the subject's welfare. Data generated as a result of this study are to be available for inspection on request by the FDA, Dendreon's representative, or the IRB. Dendreon may retain in its files copies of subject medical information required for auditing of case report forms (CRFs).

Individual subject identities will not be disclosed in any report or publication related to the study, and will not be obtained on any CRFs maintained by Dendreon.

#### **9.4 Informed Consent**

The investigator must ensure that each subject understands how the study will be conducted, and how he will participate if he so chooses. The investigator or an appropriately qualified delegate listed on FDA Form 1572 will provide a full explanation of the study and allow the subject to read the ICF and ask any questions that arise. The subject shall be given sufficient time to properly consider the information and to make an informed decision regarding consent. When all questions have been answered and the investigator or delegate is assured that the subject understands the implications of study participation, the subject will be asked to provide written consent to participate in the study by signing the ICF. The investigator or delegate will document in the subject's medical chart or progress notes that the written informed consent process occurred, including that consent was obtained prior to the initiation of study-related procedures, and will provide a copy of the signed ICF to the subject. Eligibility for the trial in which subjects are concurrently enrolled will not be affected by refusal to participate in P11-4.

The ICF, including any amendments, must be reviewed and approved by the designated IRB and by Dendreon staff or its designee. Subjects must have consented to participate in another Dendreon-sponsored trial or registry, or IIT, prior to consenting to participate in P11-4, and must sign the ICF for P11-4 prior to their first scheduled leukapheresis procedure and any blood sampling for this trial.

If an amendment to the protocol changes the subject participation schedule in scope or activity, or increases the potential risk to the subject, the ICF will be revised and submitted to the IRB for review and approval. The revised ICF should be used to obtain written consent from a subject currently participating in the study if the information is pertinent to him or per the IRB's instructions. The revised ICF will be used to obtain consent from any new subject who is enrolled in the study after the approval date of the amendment.

The subject's medical record should contain written documentation indicating that informed consent was obtained prior to study enrollment.

#### **9.5 Institutional Review Board**

The Principal Investigator is responsible for ensuring that this protocol and relevant supporting data are submitted to the appropriate IRB for review and approval before the study can be initiated. Dendreon or its designee must receive a letter documenting the IRB approval prior to initiation of the study. Amendments to the protocol will also be submitted to and approved by the IRB prior to implementation of any change(s). The Principal Investigator is also responsible

for informing the IRB of the progress of the study and for obtaining annual IRB renewal. The IRB must be informed by the Principal Investigator when the study is complete. The Principal Investigator is responsible for notifying the relevant IRB of any serious adverse event (SAE) which occurs in a subject who is participating at their site, and of any Investigational New Drug (IND) Safety Reports issued by Dendreon, per IRB policy.

## **10.0 PROTOCOL MANAGEMENT AND ADMINISTRATIVE CONSIDERATIONS**

### **10.1 Study Documentation**

The Principal Investigator and study personnel are responsible for maintaining a centralized filing system containing all study-related documentation. These files must be suitable for inspection by Dendreon, representatives of Dendreon, or the FDA at any time, and should consist of the following elements:

- Subject files, containing the completed CRFs, supporting source documentation from the medical record, and the signed ICFs.
- Regulatory files, containing the protocol with all amendments and protocol signature pages, copies of all other essential regulatory documentation, and all correspondence between the trial site, the IRB, and Dendreon.

Records are to be available for at least 5 years after study completion and the FDA is so notified.

### **10.2 Data Collection**

Trained study personnel will be responsible for entering data on the observations, tests, and assessments specified in the protocol according to the CRF Instructions. Data from the CRF will be entered into a central database and any changes will be tracked to provide an audit trail. At the completion of the study, a copy of the final clinical study report will be submitted to the FDA.

### **10.3 Protocol Interpretation and Compliance**

To ensure accurate interpretation and implementation of the study, the procedures and endpoints defined in the protocol will be carefully reviewed by the Investigator and his or her staff prior to the time of study initiation.

### **10.4 Study Monitoring**

A representative from Dendreon may visit the study site periodically to monitor adherence to the protocol, adherence to applicable FDA regulations, and the maintenance of adequate and accurate clinical records. CRFs will be reviewed to ensure that sample collection information is

recorded as specified by the protocol. The Dendreon representative will be permitted to access subject's complete medical records and other source documentation as needed to appropriately monitor the study.

